#### **7.4.2.6 Change from baseline in RLS Pain score at each time point**

The baseline visit is the measurement at Week 0.

RLS pain score and its change from baseline will be summarized by descriptive statistics, by treatment group and visit.

Least square mean difference (gabapentin enacarbil group minus placebo group) of the changes in RLS pain score from baseline will be calculated by visit, using the ANCOVA model with the baseline value as a covariate. 95% CI and two-sided p-value of the difference will be presented.

Following data will be presented graphically by treatment group:

- RLS pain score using mean (+/- SD) plot,
- Change in RLS pain score from baseline using mean (+/- SD) plot.

#### **7.4.2.7 Change from baseline in EQ-5D-5L at each time point**

The baseline visit is the measurement at Week 0.

Descriptive statistics for EQ-5D-5L VAS score and change from baseline at each visit will be presented by treatment group. For the EQ-5D-5L qualitative domains, the number and percentage of subjects in each response level value will be reported by treatment group and visit. In addition, a plot for EQ-5D-5L VAS score of mean (+/- SD) and that of change from baseline will be produced.

### **7.5 Analysis of Safety**

All analysis of safety will be presented by treatment group for the SAF, unless specified otherwise.

#### **7.5.1 Adverse Events**

An overview table will include the following details:

- Number of TEAEs,
- Number and percentage of subjects with TEAEs,
- Number of drug related TEAEs,
- Number and percentage of subjects with drug related TEAEs,
- Number of serious TEAEs,
- Number and percentage of subjects with serious TEAEs,
- Number of serious drug related TEAEs,
- Number and percentage of subjects with serious drug related TEAEs,
- Number of TEAEs leading to withdrawal of treatment,
- Number and percentage of subjects with TEAEs leading to withdrawal of treatment,
- Number of drug related TEAEs leading to withdrawal of treatment,
- Number and percentage of subjects with drug related TEAEs leading to withdrawal of treatment, and
- Number of deaths.

The number and percentage of subjects with TEAEs, as classified by SOC and PT will be summarized for each treatment group. Summaries will be provided for:

- TEAEs,
- Drug related TEAEs,
- Serious TEAEs,
- Serious drug related TEAEs,
- TEAEs leading to withdrawal of treatment,
- Drug related TEAEs leading to withdrawal of treatment,
- TEAEs excluding serious adverse event that equal to or exceed a threshold of 5.0% in any treatment group,
- Common TEAEs that equal to or exceed a threshold of 5.0% in any treatment group,
- Common drug related TEAEs that equal to or exceed a threshold of 5.0% in any treatment group.

The number of TEAEs and the number and percentage of subjects with TEAEs, as classified by SOC and PT will also be summarized by severity and by relationship to study drug. In the subject count, if a subject has multiple TEAEs with the same SOC or PT, but with differing severity or relationship, then the subject will be counted only once with the worst severity or highest degree of relationship, however, if any of the severity or relationship values are missing then the subject will be counted only once with missing severity or relationship. In the adverse event count, the adverse events will be presented in each category they were classified to. Drug related TEAEs will be presented in a similar way by severity only.

The number and percentage of subjects with TEAEs, as classified by SOC and PT will be summarized by time interval. For each adverse event in a particular interval, a subject will be counted if there is an onset of TEAEs regardless of onset in other intervals. Time intervals will be categorized according to the following categories (days from the first dosing of study drug in the treatment period):

- $\geq 1$  (0 weeks) to  $\leq 29$  (4 weeks)
- $> 29$  (4 weeks) to  $\leq 57$  (8 weeks)
- $> 57$  (8 weeks) to  $\leq 85$  (12 weeks)
- $> 85$  (12 weeks)

The number and percentage of subjects with TEAEs, as classified by SOC and PT will be summarized by subgroups defined in section 7.8.

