7.5.1 Adverse Events

AEs will be coded using the Medical Dictionary for Regulatory Activities (MedDRA). The AEs, SAEs, AEs leading to discontinuation, and AEs related to the study drug will be summarized by System Organ Class, Preferred Term, and treatment group, with tabulation of the number and percentage of subjects. In addition, the number and percentage of subjects with AE will be tabulated by severity.

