### **6.2.1 Adverse Events**

TEAE is defined as an adverse event observed after starting administration of the study drug in the treatment period. If the adverse event occurs on the date of first dose of study drug (treatment period) and the onset check box is marked “ONSET BETWEEN FIRST DOSE OF STUDY DRUG IN TREATMENT PERIOD AND FIRST DOSE OF STUDY DRUG IN FOLLOW UP PERIOD”, then the adverse event will be considered treatment-emergent.

A drug-related TEAE is defined as any TEAE with at least possible relationship to study treatment as assessed by the investigator or with missing assessment of the causal relationship.

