#### **7.5.2 Clinical Laboratory Evaluation**

The baseline visit is the measurement at Week 0.

Quantitative clinical laboratory variables, i.e. hematology, biochemistry, and thyroid function tests will be summarized in SI unit, using mean, standard deviation, minimum, maximum and

median, for each treatment group at each visit. Additionally, a within-subject change will be calculated as the post-baseline measurement minus the baseline measurement and summarized in the same way. Each laboratory result will be classified as low (L), normal (N), or high (H) at each visit according to the laboratory supplied reference ranges.

Frequency tabulations of qualitative clinical laboratory variables (urinalysis) will be presented for each treatment group at each visit.

For hematology, biochemistry and thyroid function tests, shift tables will be presented for each treatment group:

- Summary shifts of reference range changes from baseline to each visit (shift from normal or high to low, shift from normal or low to high, categorized increase [shift from low to normal or from normal to high], categorized no change [value stays in the same reference range], categorized decrease [shift from high to normal or from normal to low]).

Following data will be presented graphically by treatment group:

- Quantitative clinical laboratory test results using mean (+/- SD) plot.

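### In the SAP 7.5.1 subject count by severity, one missing value moves a subject with a known severe event to the 'missing' row

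*SAP*

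**What the plan says.** Protocol 7.5.1 promises that "the number and percentage of subjects with AE will be tabulated by severity". SAP 7.5.1 extends this to a summary by SOC and PT, by severity and by relationship, giving both the number of events and the number and percentage of subjects.

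Where a subject has several events in the same SOC or PT with differing values, "then the subject will be counted only once with the worst severity or highest degree of relationship". The same sentence then sets an exception: "if any of the severity or relationship values are missing then the subject will be counted only once with missing severity or relationship".

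Two further sentences fix its scope. For events: "In the adverse event count, the adverse events will be presented in each category they were classified to". For the drug-related subset: "Drug related TEAEs will be presented in a similar way by severity only".

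Missing causality also appears in SAP 6.2.1, which defines a drug-related event as one "with at least possible relationship to study treatment as assessed by the investigator or with missing assessment of the causal relationship".

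**The concern.** The exception discards known information. If one of a subject's events is severe, the worst severity is severe whatever the unrecorded value turns out to be. Nothing needs to be imputed, yet the subject leaves the severe row.

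The situation is foreseeable. Protocol 5.5.1 records a recurrence as a new event and treats worsening severity as a new event, so several events per subject under one PT are expected. At SOC level an incomplete minor event can displace a severe event with a different PT.

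Safety of 600 mg is the second study objective (Protocol 2.1), and the rows at stake are small. In CL-0003, moderate events occurred in 16/120 subjects on 600 mg and 7/116 on placebo. Protocol 1.4.1 reports only one severe event in the Japanese studies. In rows of that size a single misplaced subject is visible.

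**Working it through.** The plan states no figure for this rule and no expected rate of missing severity, so there is nothing to reproduce. The check applies the rule to small cases and then gives its size under stated assumptions.

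**1. Severity, one subject within one SOC or PT**

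| Recorded severities | SAP subject row | Worst non-missing | Event count (both rules) |
|---|---|---|---|
| severe, missing | missing | severe | 1 severe, 1 missing |
| mild, missing | missing | mild | 1 mild, 1 missing |
| mild, severe | severe | severe | 1 mild, 1 severe |
| missing only | missing | missing | 1 missing |

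The rules differ only when known and missing values are mixed. For {severe, missing} the SAP row is wrong with certainty. For {moderate, missing} or {mild, missing} the worst known value is a lower bound, because the unrecorded event could be worse. That is why the fix includes a footnote.

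**2. Relationship, set against SAP 6.2.1**

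I take 'not assessable' as related, as Protocol 5.5.3 does.

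| Recorded relationships | SAP 7.5.1 row | Drug-related under 6.2.1? | Highest non-missing |
|---|---|---|---|
| probable, missing | missing | yes | probable |
| possible, missing | missing | yes | possible |
| not related, missing | missing | yes | not related |
| not related only | not related | no | not related |

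Under the SAP rule, the related rows plus the 'missing' row equal the drug-related subject count, so the tables reconcile. What is lost is the known 'probable' subject, shown as 'missing'. A plain switch to the highest non-missing relationship would place {not related, missing} under 'not related' while 6.2.1 still counts that subject as drug-related, and reconciliation would fail.

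**3. Size**

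Assume each event lacks severity independently with probability q, and that a subject with a known severe event has m other events in the same SOC or PT. The chance of being moved is 1 − (1 − q)^m:

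| q | m = 1 | m = 2 | m = 3 |
|---|---|---|---|
| 0.5% | 0.5% | 1.0% | 1.5% |
| 1% | 1.0% | 2.0% | 3.0% |
| 2% | 2.0% | 4.0% | 5.9% |
| 5% | 5.0% | 9.8% | 14.3% |

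Each subject moved is 1/180 = 0.56 percentage points of an arm.

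For a rough ceiling on the moderate row, suppose the CL-0003 rate on 600 mg recurs: 180 × 16/120 = 24 subjects. If all 24 fell in one SOC and each had three other events there, the expected number moved would be 24 × 0.0297 = 0.7 at q = 1%, and 24 × 0.1426 = 3.4 (3.4/180 = 1.9 percentage points) at q = 5%. The 16/120 covers all SOCs, whereas the rule acts within one SOC or PT, so real rows would be smaller.

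**The case against.** The strongest reply is that the trigger should be rare. Protocol 5.5.4 requires a severity for each event. Protocol 5.5.1 makes severity and causality eCRF items for treatment-period and follow-up events. 'Not assessable' is a recordable causality category (5.5.3), so an uncertain investigator need not leave a blank. Sites must ensure complete data (8.1.1), and codes are opened only after lock (4.4.3). This stands, and it limits the size of the problem. It does not justify a rule that misplaces a known severe case whenever it operates.

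Several stronger readings are tempting and are not supported:

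- *The severe event is lost.* It is not. The event count keeps each event in its own category, and the subject moves to a visible 'missing' row. The serious, overall drug-related and withdrawal tables are not split by severity or relationship. The one severe event in Protocol 1.4.1, a fatal lymphoma at 1200 mg in the long-term study, would have met the seriousness criteria in any case.
- *The relationship rule contradicts SAP 6.2.1.* The second table above shows that the counts reconcile.
- *Any loss falls on the active arm.* More events per subject give more chances of a missing field, but the documents give no missing rate by arm, so a differential effect is conjecture.
- *The laboratory shift summary in SAP 7.5.2 has the same fault.* The "categorized increase [shift from low to normal or from normal to high" category does omit low-to-high, and the decrease category omits high-to-low. However, the same list has separate categories for a shift from normal or low to high and from normal or high to low, so those shifts are reported.

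**Conclusion.** The point holds for subject counts by category. In the severity tables for all treatment-emergent events and for drug-related events, a subject with a known severe event can be counted as 'missing', which understates the severe row. The moderate row can be understated in the same way where moderate is the worst known value. In the relationship table a known 'probable' subject can likewise leave that row, although the related total still agrees with SAP 6.2.1.

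The practical effect is probably small, and it is zero with complete fields at lock. The illustrative 1% to 3% rests on an assumed 1% missing per event, independence, and one to three other events in the SOC or PT; none of these comes from the documents. The primary efficacy analysis and overall adverse event incidence are not touched. The correction is worth making because the rule is wrong each time it acts on a known severe event, and correcting it costs little.

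**What to change.** In SAP 7.5.1:

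1. **Severity.** Count the subject once at the worst non-missing severity within the SOC or PT. Use 'missing' only when all of that subject's events there lack severity. Apply this to all treatment-emergent events and to drug-related events.
2. **Footnote.** Give, by arm, the number of subjects with any missing severity or relationship, so that rows resting on a lower bound are visible.
3. **Relationship.** Keep a subject with a known 'probable' event in the 'probable' row. Put a subject whose only other values are 'not related' in a row labelled 'missing (treated as related)'. For {possible, missing} either related row reconciles; the SAP should name one. The related rows plus the 'missing' row will then still equal the SAP 6.2.1 count.

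The cost is a few sentences in the SAP and a small change to the adverse event table program. No new data are needed. No change to SAP 7.5.2 is needed on this account.

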#### **7.5.1.1 Adverse Events of special interest**

For the adverse events of Nervous system disorders, the following analysis will be performed:

- The number and percentage of subjects with TEAEs of Nervous system disorders, as classified by SOC and PT will be summarized for each treatment group,
- Time to first onset of selected TEAE using a Kaplan-Meier plot based on the date of first dosing of study drug in the treatment period. Subjects who complete the study without having any TEAEs of Nervous system disorders will be censored at the date of last evaluation. Subjects who discontinued the study without having any TEAEs of Nervous system disorders will be censored at the date of discontinuation.

The following PT terms are defined as TEAEs of Nervous system disorders:

PT term	PT code
Somnolence	10041349
Dizziness	10013573

#### **7.5.2 Clinical Laboratory Evaluation**

The baseline visit is the measurement at Week 0.

Quantitative clinical laboratory variables, i.e. hematology, biochemistry, and thyroid function tests will be summarized in SI unit, using mean, standard deviation, minimum, maximum and

median, for each treatment group at each visit. Additionally, a within-subject change will be calculated as the post-baseline measurement minus the baseline measurement and summarized in the same way. Each laboratory result will be classified as low (L), normal (N), or high (H) at each visit according to the laboratory supplied reference ranges.

Frequency tabulations of qualitative clinical laboratory variables (urinalysis) will be presented for each treatment group at each visit.

For hematology, biochemistry and thyroid function tests, shift tables will be presented for each treatment group:

- Summary shifts of reference range changes from baseline to each visit (shift from normal or high to low, shift from normal or low to high, categorized increase [shift from low to normal or from normal to high], categorized no change [value stays in the same reference range], categorized decrease [shift from high to normal or from normal to low]).

Following data will be presented graphically by treatment group:

- Quantitative clinical laboratory test results using mean (+/- SD) plot.

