## 7 STATISTICAL METHODOLOGY

### 7.1 General Considerations

- For continuous variables, descriptive statistics will include the number of subjects (n), mean, standard deviation, median, minimum and maximum.
- The number of digits to be used for the mean, standard deviation and median will be added one more digit to raw data with rounding off. The minimum and maximum will be presented with the same number of digit(s) as raw data.
- Frequencies and percentages will be displayed for categorical data. Percentages by categories will be based on the number of subjects with no missing data, i.e. will add up to 100%.
- Frequencies and percentages will be rounded to one decimal place.

- For time-to-event variables, the number and percentage of subjects with the event using Kaplan-Meier method, the cumulative event rate will be estimated and a plot will be constructed.
- All data processing, summarization, and analyses will be performed using SAS Drug Development version 4.5 and SAS version 9.4. Specifications for tables, figures, and data listing formats can be found in the TLF specifications for this study.
- For continuous variables that are recorded as “< X” or “> X”, the value of “X” will be used in the calculation of summary statistics. The original values will be used for the listings.
- MedDRA/J (version 19.0) will be used as the coding dictionary for adverse event and medical history.
- WHODDE (J-Drug(2016H1)) will be used as the coding dictionary for previous and concomitant medication.
- All statistical results will be presented, as appropriate, by treatment group, and by scheduled visit; the schedule of assessments is provided in section [7.10](#)
- For the definition of subgroups of interest please refer to section [7.8](#)

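### In the laboratory shift summary (SAP 7.5.2), low-to-high belongs to none of increase, no change or decrease, and neither does high-to-low

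*SAP*

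**What the plan says.** SAP 7.5.2 (Clinical Laboratory Evaluation) takes Week 0 as baseline and states: "Each laboratory result will be classified as low (L), normal (N), or high (H) at each visit". For hematology, biochemistry and thyroid function tests it then lists five shift summaries from baseline to each visit in one bullet:

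- Two rows for arrival at an abnormal range: "shift from normal or high to low, shift from normal or low to high".
- An increase row: "categorized increase [shift from low to normal or from normal to high".
- A no-change row: "categorized no change [value stays in the same reference range".
- A decrease row: "categorized decrease [shift from high to normal or from normal to low".

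SAP 7.1 (General Considerations) sets the general rule for categorical data: "Percentages by categories will be based on the number of subjects with no missing data, i.e. will add up to 100" per cent.

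Protocol 7.5.2 asks for shift tables against the normal ranges at each treatment-period time point. It does not define increase, no change or decrease, so it does not settle the matter.

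**The concern.** The last three rows share a label and run increase, no change, decrease, so a reader will take them as a complete classification by direction. The first two rows show that the authors had two-range shifts in mind, because each names both starting ranges. The bracketed definitions of increase and decrease name one-range moves only. The shifts left without a direction are therefore the two that cross the whole normal range.

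At stake is whether a descriptive safety table is internally coherent. A subject can be counted as having shifted to high without being counted as increased. The programmer must either leave that subject out of the three rows or depart from the written definition.

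**Working it through.** **Inputs.** There are three states (L, N, H) at baseline and three at the visit, so 3 × 3 = 9 combinations. The row definitions are those of SAP 7.5.2, taken literally. The plan states no figure of its own to reproduce.

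**Assignment of each combination.**

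| Baseline → visit | Shift to low | Shift to high | Increase / no change / decrease |
|---|---|---|---|
| L → L | – | – | no change |
| L → N | – | – | increase |
| L → H | – | yes | **none** |
| N → L | yes | – | decrease |
| N → N | – | – | no change |
| N → H | – | yes | increase |
| H → L | yes | – | **none** |
| H → N | – | – | decrease |
| H → H | – | – | no change |

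Increase, no change and decrease cover 2 + 3 + 2 = 7 of 9. The two left over are L → H and H → L. All 9 combinations appear in at least one of the five rows, because these two are caught by the shift-to-high and shift-to-low rows.

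**Effect on the percentages.** If k of n subjects with data have a two-range shift, the three rows sum to (n − k)/n. With k = 0 the sum is 100%. With k = 1 and n = 180 (planned per arm) it is 179/180 = 99.4%. With n = 180 × 0.85 = 153 (after the planned discontinuation of about 15%) it is 152/153 = 99.3%. SAP 7.1 reports percentages to one decimal place, so three rounded rows can be off by at most 3 × 0.05 = 0.15 points. Rounding would not explain the shortfall.

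**Consistency between rows.** Increase counts (L → N) + (N → H). Shift to high counts (N → H) + (L → H). The increase row is the smaller of the two whenever L → H outnumbers L → N for that test and visit.

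**How often.** The documents give no low or high rates. As a pure illustration, suppose status is independent between baseline and visit. The unclassified share is then 2 × P(low) × P(high). At 2.5% low and 2.5% high it is 2 × 0.025 × 0.025 = 0.125%, or 0.2 of 180 subjects per test and visit. At 5% and 10% it is 2 × 0.05 × 0.10 = 1%, or 1.8 of 180. Positive correlation within subjects makes opposite extremes rarer than this. These rates are assumptions, and the finding does not rest on them.

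**After the change.** With L → H added to increase and H → L to decrease, coverage is 3 + 3 + 3 = 9 of 9, with no overlap.

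**The case against.** The strongest case on the other side is that nothing disappears from the safety output. This stands. Both two-range shifts are counted in the shift-to-high and shift-to-low rows. The section also reports within-subject change with its minimum and maximum, SAP 7.5.2.1 has its own liver thresholds, and Protocol 5.5.1 makes abnormalities that the investigator judges clinically significant into adverse events. A reader might infer that the table as a whole hides the most extreme laboratory changes. It does not: the understatement is confined to two of five rows.

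A reader might also infer that the SAP defines an upward shift in two conflicting ways. It does not. Shift to high counts subjects who become high. Increase counts upward movement between ranges, including low to normal. The rows measure different things and are meant to overlap, so the fault is incomplete coverage.

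Nor is it right that the three percentages can never reach 100%. They fail only when a two-range shift occurs. The rule in SAP 7.1 is general and does not name this table. That the three rows should partition the subjects is an inference from their labels, though a natural one.

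It is tempting to multiply an assumed share over every test and visit with 180 subjects per arm and report a large total. The documents do not support that. They give no rates, independence between visits inflates opposite extremes, and about 15% of subjects are expected to discontinue. Candidates with clinically relevant laboratory abnormalities are also excluded at formal registration (criteria 17 and 20).

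Finally, the separate table specifications mentioned in SAP 7.1 are not available here and may resolve the rows. That would not correct the SAP wording.

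**Conclusion.** Wrong as written, and minor. The gap of two combinations in nine is exact and follows from the SAP's own definitions. No other text in either document assigns low-to-high or high-to-low to one of the three rows. Whenever such a shift occurs, the subject is unclassified by direction, the increase or decrease row is understated, and the three percentages depart from the general rule in SAP 7.1. The number of subjects affected cannot be computed from the documents and is probably small. No test, estimate, efficacy result or liver criterion depends on it. The conclusion assumes only that the three rows are meant as a complete classification and are programmed as worded.

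**What to change.** In SAP 7.5.2, define increase as low to normal, low to high or normal to high, and decrease as high to normal, high to low or normal to low. Leave no change and the shift-to-high and shift-to-low rows as they are. Check that the table specifications and program follow the new wording. The cost is one line of SAP text and a small programming check. Design, data collection and inference are unaffected.
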